#### **Sub-study 1c:**

This sub-study will include 266 subjects as well as an additional 53 participants to account for an anticipated 20% rate of study dropout. Number of subjects was adjusted due to recent introduction of the vaccination booster shot and availability of extra funding which allows us to expend study aims to further test of the treatment efficacy.

For other objectives of sub-study 1c, sample size was determined using the RMASS program (<http://tigger.uic.edu/~hedecker/ml.html>)

Based on our sample size estimation, we are confident that the enrollment of 66 (1a/1b) or 266 (1c) participants will provide a sufficient number of subjects to evaluate these outcomes with medium effect size while also ascertaining safety (Tubert-Bitter et al., 2000; Zhang P, 2003).

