## **9. RESEARCH DESIGN AND METHODS**

The following research design applies to each of the following studies:

Sub-study 1a: FoTv vs. placebo for acute COVID-19 patients

Sub-study 1b: QFPD vs. placebo for acute COVID-19 patients

Sub-study 1c: FoTv vs. placebo as an adjunct to COVID-19 vaccination

Sub-studies 1a and 1b of Phase 1 trial will each be 2-arm multicenter double blind randomized placebo controlled clinical trials.

Each of these safety/feasibility sub-studies will be conducted identically with the exception of additional exclusion criteria that will be required for sub-study 1b on account of the presence of herbal components including ephedrine that require these precautions for avoiding herb-drug interactions.

Sub-study 1c will be a single site double blind randomized placebo controlled clinical trial.

This will be a shorter intervention with broader inclusion criteria.

The research design and methods for the larger efficacy trial (Phase 2) will require analysis of these first two feasibility studies, and the final protocol will be submitted as a future amendment.

The primary objective of sub-studies 1a and 1b will be to assess the safety of FoTv or mQFPD, respectively, when used as therapies for acute COVID-19 infection and feasibility of the study protocol.

The primary objectives of sub-study 1c will be to ascertain the safety of FoTv when used as an adjunct to standard COVID vaccination as well as to evaluate its effects on post-vaccine COVID-19 antibody titers and on vaccination-related side effects.

A total of 66 subjects (33 FoTv or mQFPD and 33 placebo) will be enrolled in each of the 1a and 1b sub-studies.

A total of 266 subjects (133 FoTv and 133 placebo) will be enrolled in sub-study 1c.

The study protocol will be implemented and safety, feasibility, clinical, and laboratory data will be collected.

Interested participants will be asked to contact the study team, who will then conduct screening, consenting, and study enrollment. The study will be open to patients who are

- a) Mildly-to-moderately symptomatic and have tested positive for COVID-19 (sub-studies 1a and 1b)
- b) Scheduled for COVID-19 vaccination (sub-study 1c).

See section 11 for recruitment plan.

Once their eligibility has been confirmed, participants will be randomized to one of two groups by the study statistician:

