- Group 1 – either Mycelium of *Fomitopsis officinalis* and *Trametes versicolor* (FoTv) for sub-studies 1a and 1c or modified Qing Fei Pai Du Tang (mQFPD) for sub-study 1b
- Group 2 - Inert placebo (encapsulated brown rice)

We anticipate screening approximately 90 or 75 potential candidates per sub-study in order to consent and enroll 66 or 48 participants to account for up to 20% drop-out rate.

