### **Sample Size Justification:**

We anticipate screening approximately 90 or 300 potential candidates for each sub-study in order to consent and enroll 66 or 266 participants per study 1a/b or 1c respectively.

The primary focus of sub-studies 1b and 1c, as with sub-study 1a, will be on ascertainment of the safety of the natural products under study. The study 1c will also examine efficacy of the mushroom blend.

Therefore, like sub-study 1a, sub-study 1b will also include 27 participants per arm as well as an additional 6 participants per arm to account for an anticipated 20% rate of study dropout. Thus,  $N = (33/\text{arm} \times 2 \text{ arms}) = 66$ .

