## 10. HUMAN SUBJECTS

Sub-study 1a Fo-Tv vs. placebo:

66 total patients (N=27 in each of two study arms: FoTv and placebo plus an additional 20% per arm to guard against dropout) who have tested positive for COVID-19 and are mildly-to-moderately symptomatic will be included in the study.

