#### **Exclusion Criteria**

1. Any of the following symptoms which, according to the CDC, require hospitalization:
  - a. Trouble breathing
  - b. Persistent pain or pressure in the chest
  - c. New confusion or inability to arouse
  - d. Bluish lips or face
2. Current use of investigational agents to prevent or treat COVID-19
3. Prisoners
4. Known liver disease (ALT/AST >3x ULN or diagnosis of cirrhosis)
5. Known renal disease (eGFR < 60 ml/min) or acute nephritis.
6. Uncontrolled hypertension (SBP>140 or DBP>90 while on medications)
7. Pregnant or breastfeeding women
8. Allergy to tree nuts
9. Bleeding dyscrasia or on anticoagulation (aspirin and/or clopidogrel is allowed)
10. Use of Tolbutamide
11. Use of systemic corticosteroids (hydrocortisone, cortisone, prednisolone, betamethasone, methylprednisolone, prednisone, dexamethasone). Inhaled budesonide is to be allowed.
12. Use of digoxin
13. Use of Oxacillin
14. Use of Interferon

15. Use of Vincristine
16. Use of Cyclosporine
17. Use of Amiodarone
18. Patients with a past medical history of epilepsy
19. Use of monoamine oxidase inhibitors (MAOI)
20. Use of Methamphetamine within the prior 30 days
21. Use of Cocaine within the prior 30 days
22. Use of aminoglycosides, carbamazepine, flecainide, lithium, phenytoin, phenobarbital, rifampicin, theophylline and warfarin

Sub-study 1c Fo-Tv vs. placebo:

266 total patients who are receiving COVID-19 vaccination will be included in the study.

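### Sub-study 1c has contradictory sample sizes: one sentence adds 53 to 266 for dropout, four others give 266 as the enrolled or total number, and a further sentence gives an enrolment of 48 that fits no sub-study

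*Combined protocol and SAP*

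**What the plan says.** Under Sample Size Justification, the sub-study 1c paragraph in Section 9 opens: "This sub-study will include 266 subjects as well as an additional 53 participants to account for an anticipated 20% rate of study dropout".

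Four statements give 266 as the enrolled or total number:

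- Section 9, Research Design and Methods: "A total of 266 subjects (133 FoTv and 133 placebo) will be enrolled in sub-study 1c".
- Section 9, Sample Size Justification, first sentence: "We anticipate screening approximately 90 or 300 potential candidates for each sub-study in order to consent and enroll 66 or 266 participants".
- The closing paragraph of the same sub-study 1c text: "we are confident that the enrollment of 66 (1a/1b) or 266 (1c) participants will provide a sufficient number of subjects".
- Section 10, Human Subjects, sub-study 1c: "266 total patients who are receiving COVID-19 vaccination will be included in the study".

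For the smaller sub-studies the dropout allowance sits inside the stated total. The Sample Size Justification says "sub-study 1b will also include 27 participants per arm as well as an additional 6 participants per arm", making 66. Section 10 describes 1a as "66 total patients (N=27 in each of two study arms: FoTv and placebo plus an additional 20% per arm to guard against dropout". The Section 10 line for 1c has no such dropout clause.

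A separate Section 9 paragraph, just after the two treatment groups are listed, says: "We anticipate screening approximately 90 or 75 potential candidates per sub-study in order to consent and enroll 66 or 48 participants". It ties these figures to a dropout rate of up to 20%.

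**The concern.** The sub-study 1c text disagrees with itself within a few lines. It starts from 266 with 53 more on top and ends by resting the adequacy of the sample on 266 enrolled. A reader cannot tell whether 266 is the number randomised or the number to be left after dropout.

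The enrolment target, the screening plan and the randomisation list all depend on one figure. Sub-study 1c is also the one for which Section 9 claims enough subjects to test efficacy, so its number should be unambiguous. The paragraph with 48 enrolled from 75 screened adds a second conflict, because it cannot be matched to 1a, 1b or 1c.

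**Working it through.** **Inputs.** Sub-study 1c: base 266, add-on 53, dropout 20%, about 300 screened (Sample Size Justification); 133 per arm (Section 9 design text). Sub-studies 1a and 1b: 27 per arm, 6 added per arm, 66 in total.

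**1. Reproduce the plan's 53.** 0.20 × 266 = 53.2, rounded to 53. The figure reproduces as a simple add-on to a base of 266.

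**2. The implied total.** 266 + 53 = 319.

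- Against screening: 319 − 300 = 19 more than the approximate number to be screened.
- Against equal arms: 319 / 2 = 159.5.
- Neither conflict arises at 266 enrolled: 266 is below 300, and 266 / 2 = 133.

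**3. The rule used for 1a and 1b.** 27 × 1.20 = 32.4, rounded up to 33; 33 × 2 = 66 enrolled. Dividing by the retention rate would give 27 / 0.8 = 33.75, so 34, which the plan does not use. The document's rule is therefore to add 20% of the base and quote the total with the allowance inside.

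**4. Apply that rule to 1c.**

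- If 266 is the base, the add-on is 53 and the total is 319.
- If 266 is the total, the base is about 222 (222 × 1.20 = 266.4) and the add-on is 266 − 222 = 44, not 53.
- By the other convention, 266 − 53 = 213 and 213 / 0.8 = 266.25, so 53 also fits as 20% of an enrolled 266.

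The number 53 therefore does not settle which reading was intended.

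**5. Expected completers at 20% dropout.**

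| Enrolled | Calculation | Completing |
|---|---|---|
| 266 | 266 × 0.8 = 212.8 | about 213 (106 per arm) |
| 319 | 319 × 0.8 = 255.2 | about 255 |
| 334 | 334 × 0.8 = 267.2 | about 267 |

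To retain 266: 266 / 0.8 = 332.5, so 333, or 334 with equal arms. If 266 must be retained, 53 extra participants cover only 53 / 319 = 16.6% dropout, and 255.2 is (266 − 255.2) / 266 = 4.1% short.

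**6. The other Section 9 figures.** 66 or 48 enrolled from 90 or 75 screened, against 66 or 266 from 90 or 300 in the Sample Size Justification. The first member of each pair agrees; the second does not, and no sub-study enrols 48.

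**7. Does the ambiguity threaten power?** The plan gives no numeric effect size, power, standard deviation or correlation, so its RMASS calculation cannot be reproduced. As an illustration only, assume a simple two-sample comparison of means, two-sided alpha 0.05, no multiplicity adjustment, and a standardised difference of 0.5 for a medium effect. Power is about 0.95 with 106 per arm and 0.98 with 133 per arm. Under the same design, the difference detectable with 80% power is 0.38 and 0.34 respectively.

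**The case against.** The strongest reply is that the ambiguity is narrow. Four statements say 266 enrolled or total, the adequacy claim is itself tied to enrolment, and 319 is never printed. One sentence is out of line, and the excess over the screening number arises only if 319 is assumed. This stands as far as it goes: the weight of the text is with 266 enrolled. It does not dispose of the point. The outlying sentence has the same form as the 1b sentence, where the first number is the one before dropout, and 53 is what the plan's add-on rule gives on a base of 266.

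A reader might instead infer that 53 is simply the right allowance inside 266 and that only the linking words are wrong. The documents do not support that. Under the rule they use for 1a and 1b, an inclusive 266 would be about 222 plus 44.

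It is also fair to object that about 213 is not the analysis number. Section 9, Statistical Methods and Considerations, analyses all randomised subjects, and the confirming mixed model keeps those with missing data or early termination. The rank tests are described as using complete data. If run visit by visit, they would use everyone with data at that visit, so 213 is a worst case for those tests.

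Finally, the figure of 48 carries no sub-study label. Linking it to 1c rests only on its position in the sentence. It is nevertheless wrong for all three sub-studies.

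**Conclusion.** The sample-size statements for sub-study 1c contradict each other and should be corrected. The gap is 53 participants: 266 against an implied 319. The text favours 266 enrolled but does not exclude 266 as the number to be retained, and only the sponsor can say which was meant. The completing numbers above assume the stated 20% dropout, which another Section 9 paragraph treats as an upper limit.

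A reader might infer that sub-study 1c is underpowered, or that the RMASS calculation must be redone. Neither follows. The plan gives none of the RMASS inputs, so nothing shows that the calculation was based on completers. All randomised subjects are to be analysed, and the illustration keeps power at about 95% or more for a difference of 0.5 with either 106 or 133 per arm. The charge that 53 is too few applies only if 266 was meant as the number retained.

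**What to change.** State one enrolment target for sub-study 1c, say whether it includes the dropout allowance, and use it in the Section 9 design text, both screening sentences, the Sample Size Justification with its 1c paragraph, and Section 10.

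- **If 266 is the enrolled number:** delete the clause adding 53. State that at 20% dropout about 213 (106 per arm) would complete all follow-up. Note that this is a worst case for the complete-data rank tests, while the mixed model and the main analysis rule use all randomised subjects. Cost: wording only, no added patients.
- **If 266 was the number to be retained:** correct enrolment to 333 (334 with equal arms) and revise the screening figure. Alternatively, keep 319, restate the retained number as about 255, and correct the screening figure and arm sizes. Cost: added enrolment and screening.

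In either case, replace the Section 9 figures of 90 or 75 screened and 66 or 48 enrolled with the reconciled ones. If 266 is enrolled, these are 90 or 300 screened and 66 or 266 enrolled. No new sample-size calculation is needed for this correction.

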### **Clinical Laboratory Measurements:**

Sub-studies 1a and 1b:

Sample collection (nasal swab and approximately 25 mL of whole blood with an additional 50 mL whole blood optional) will occur at two time points: (1) screening/baseline and (2) end-of-study. The purpose of the time point (1) sample collection will be to obtain specimens for both screening and baseline clinical laboratory tests. The additional 50 mL of whole blood will allow for in-depth analysis of the peripheral mononuclear cell, including rare immune cell subsets. This collection is optional. The purpose of the time point (2) sample collection will be to obtain specimens for end-of-study clinical laboratory tests.

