required methodological modifications. The safety data will be summarized by treatment group and site. Adverse events will be tabulated. These will include the number of participants for whom the event occurred, the rate of occurrence, and the severity and relationship of adverse events to study treatment. Safety data will be analyzed using ANOVAs for continuous variables and Chi-square analyses for dichotomous variables at each time point. Wilcoxon-Mann-Whitney rank-sum test will be used to analyze treatment arm versus control arm across study visits and sites. We anticipate using non-parametric tests because the majority of the outcome measures used in our research may not be normally distributed. The Kruskal-Wallis test will be used to determine whether samples from each of the two arms originated from the same distribution. Since nonparametric tests are based on complete data and ignore missing follow-up data, general linear mixed regression modeling (Gibbons et al, 1988; Hedeker et al, 199; Laird et al, 1982) will be used to confirm the results of the nonparametric tests. The two arms will be compared over time with a focus on the treatment by Time interaction effect. Mixed regression modeling offers robust handling of missing data (Little, 1996) with an assumption that the data is missing at random. This method allows the inclusion of subjects with missing data or those who were terminated early in the study, without relying on data imputation procedures. This method provides an estimate of the individual variability around the population trend, the variability of the individual intercepts (baseline values) and slopes (changes across time), and the correlation between them. Co-variance structure will be chosen based on Akaike's Information Criterion (AIC). Random group level treatment effects will also be evaluated for importance based on the model AIC. Denominator degrees of freedom will be calculated using the Kenward-Roger small sample correction.

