A detailed list of feasibility outcomes is provided in the previous section. Briefly, feasibility outcomes will be assessed by determining: 1) Numbers of potentially eligible and ineligible patients, number contacted, and consent rates. 2) Feasibility of recruiting sites in which staff are interested in participating in a future main trial. 3) Rate of retention in the trial, including response rates to questionnaires and individual measures. 4) Intervention fidelity and adherence using case report forms and patient-completed personal diaries. 5) Determining the primary outcome measure for the main trial by assessing and comparing sensitivity to change of the measures and other statistical properties, comparing follow-up rates of different methods of data capture and of individual measures, and evaluating which outcome measures best reflect the patients' recovery goals, as identified from the collected data.

As indicated above, the primary aims of our data analytic strategy for sub-studies 1a and 1b will be directed toward examining the safety and feasibility of the treatments. Although it is not our major focus, we also aim to estimate effect sizes to assist in future power calculations. However, recent work by Kraemer (2006) has highlighted important limitations of this aim due to the large standard error surrounding the pilot study effect size. As a result, the primary focus of our analyses will remain on safety and feasibility and we will report our findings with this limitation in mind. Our goal is to collect important data regarding our ability to implement recruitment strategies, and the safety and feasibility of the treatments and measurements. Information derived from this research will lead to better-designed full-scale studies and help inform decisions regarding whether it is worthwhile to commit additional resources to future treatment development. Due to our small sample size, our statistical analytical findings will be interpreted with caution. Sub-study 1c will include sufficient number of subjects to test for treatment efficacy.

Data will be analyzed from all randomized subjects. All statistical tests will be two-tailed. Differences will be considered statistically significant provided a p-value of 0.05 or less is obtained. The significance level for the tests will be adjusted with a Bonferroni correction for multiple comparisons, if needed. Data will be analyzed using SPSS version 27.

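### The statement that 66 participants suffice for a medium effect in sub-studies 1a and 1b has no reported inputs, and the planned per-time-point tests fall short of a conventional 80% power

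*Combined protocol and SAP*

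**What the plan says.** All references are to the combined protocol and SAP, Section 9 unless stated.

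- **Size of 1a and 1b.** Sample Size Justification: "like sub-study 1a, sub-study 1b will also include 27 participants per arm as well as an additional 6 participants per arm", the 6 being for an anticipated 20% dropout. This gives 33 per arm and 66 in total. Nothing is given behind the 27.
- **Sizing method.** The Sub-study 1c paragraph: "For other objectives of sub-study 1c, sample size was determined using the RMASS program". No program is named for 1a or 1b.
- **The sufficiency statement.** The same paragraph refers to a sample size estimation, expresses confidence in it, and concludes, with safety included in the claim, that "enrollment of 66 (1a/1b) or 266 (1c) participants will provide a sufficient number of subjects to evaluate these outcomes with medium effect size". It cites two references. By their titles in Section 22, both concern sample size for equivalence testing.
- **Planned tests.** Statistical Methods And Considerations: "Safety data will be analyzed using ANOVAs for continuous variables and Chi-square analyses for dichotomous variables at each time point". Rank tests are expected as well, with a mixed model to confirm them: "The two arms will be compared over time with a focus on the treatment by Time interaction effect".
- **Planned safety tables.** The same section lists what the event tables hold: "These will include the number of participants for whom the event occurred, the rate of occurrence, and the severity and relationship of adverse events".
- **The plan's own caution.** The same section makes safety and feasibility the focus of 1a and 1b, warns of the large standard error of a pilot effect size, and says: "Due to our small sample size, our statistical analytical findings will be interpreted with caution". It then states that 1c has enough subjects to test efficacy, and makes no such statement for 1a or 1b.

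**The concern.** The sufficiency sentence stands under the 1c heading, and its outcomes are not defined for 1a and 1b, but it names their 66 participants explicitly. A reader cannot reconstruct the claim, because no effect, power, standard deviation, event rate, margin or correlation is reported for those sub-studies. It also sits badly with the later text, which treats the same sample as small.

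Safety is a primary objective of 1a and 1b, and the synopsis (Section 5) makes the Phase 2 study follow once safety and feasibility are established. Significance tests on safety data are planned, with no interval and no margin. If such a test is non-significant, a statement that the sample was sufficient could lend it more weight than 27 to 33 per arm can carry.

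**Working it through.** **Inputs from the documents.** Two-sided tests at 0.05 (Statistical Methods And Considerations); 1:1 allocation; 27 per arm before and 33 per arm after the dropout allowance.

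**Assumed, because the documents give no figure.** Medium means d = 0.5 for continuous outcomes and w = 0.3 for dichotomous ones. The benchmark is 80% power. Any Bonferroni correction is left out; it would only lower the power.

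**1. The plan's own figure.** 27 × 1.2 = 32.4, rounded up to 33; 33 × 2 = 66. The stated total reproduces. (Dividing instead, 27/0.8 = 33.75, gives 34 per arm and 68 in total, a difference of two.) The 27 itself follows from no stated input.

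**2. ANOVA at one time point** (with two arms, a t-test). Noncentrality = d√(n/2).
- n = 27: 0.5 × √13.5 = 1.84; power 43.8%.
- n = 33: 0.5 × √16.5 = 2.03; power 51.6%.
- 80% power needs 64 evaluable per arm.
- The difference detectable with 80% power is d = 0.78 (27) or 0.70 (33). For a rank test with relative efficiency 0.955, divide by √0.955: about 0.80 or 0.72.

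**3. Chi-square at one time point.** Noncentrality = N·w².
- N = 54: 54 × 0.09 = 4.86; power 59.7%.
- N = 66: 66 × 0.09 = 5.94; power 68.3%.
- If medium is taken as h = 0.5 instead, power is 45% or 53%.

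**4. Treatment-by-time with two blood draws.** Routine sampling in 1a and 1b "will occur at two time points: (1) screening/baseline and (2) end-of-study". With two measurements the interaction is a comparison of change scores, so the effect is d/√(2(1 − r)), where r is the baseline-to-Day-14 correlation.

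| r | 27 per arm | 33 per arm |
|---|---|---|
| 0.3 | 33% | 39% |
| 0.5 | 44% | 52% |
| 0.7 | 64% | 73% |
| 0.8 | 81% | 89% |

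80% is reached at r of about 0.79 (27) or 0.75 (33). Adjusting Day 14 for baseline, with effect d/√(1 − r²), it is reached at about 0.77 or 0.70.

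**5. Daily diary.** The result depends on the correlation structure.
- Unadjusted mean of 14 days, constant correlation r, effect d/√((1 + 13r)/14): at r = 0.3/0.5/0.7, power is 86/69/56% (27) or 92/78/65% (33).
- Linear treatment-by-time over days 0–14, reaching d = 0.5 at day 14, with 27 per arm: 73% to 98% under constant correlation 0.3 to 0.7, but 27% to 31% under day-to-day decay (AR(1), 0.7 to 0.9).

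**6. Rare events.** With no event in an arm, the one-sided 95% upper bound is 1 − 0.05^(1/n): 10.5% (27) or 8.7% (33).

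**The case against.** **There is a stated basis.** A reader might infer that the claim rests on nothing. The documents do not support that: they refer to a sample size estimation and cite two references. What stands is narrower. No calculation or input is reported for 1a or 1b, and the plan contains no equivalence margin or equivalence test to which those references could apply.

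**The benchmark is imported.** This stands. No power target is set, so falling short means short of an assumed 80%. Likewise, 44% and 52% describe the ANOVA only; the chi-square figures at w = 0.3 are higher, though still below 80%.

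**The repeated-measures analyses may do better.** This stands too. It would be tempting to say that 66 participants are too few for every planned analysis. Steps 4 and 5 show that some reach 80% and others do not, depending on correlations that the documents omit. The two-draw figures also do not cover everything collected: swab or saliva samples are taken at days 0, 7 and 14, and hospitalized participants' laboratory values come from admission records.

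**The plan already guards against over-reading.** Largely fair. It tabulates events, asks for caution, has a DSMB (Section 15), and leaves the Phase 2 protocol to a later amendment that follows analysis of 1a and 1b. A reader might infer that a non-significant difference will be taken as proof of safety; no text says so. The remaining risk is one of interpretation.

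**The sentence belongs to 1c.** Its position suggests so, but it names 66 for 1a/1b, and a reader will apply it there. The tension with the later text is between two assertions, not two numbers.

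**Conclusion.** The concern holds in limited form. For 1a and 1b the medium-effect statement is unsupported by any reported calculation or input, and it conflicts in tone with the plan's own caution about the small sample. Against an assumed 80%, the ANOVA at a single time point has 44% to 52% power at an assumed d = 0.5, and the chi-square test about 60% to 68% at an assumed w = 0.3. Whether the repeated-measures analyses meet the statement cannot be determined from the documents.

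The total of 66 is not an arithmetic error. The 1c half of the sentence is not challenged: at d = 0.5, a single comparison in 1c has about 98% power with 133 per arm, and about 95% with the 106 per arm left if 20% of the 266 drop out. The point should be corrected, but it does not invalidate 1a or 1b as safety and feasibility studies.

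**What to change.** 1. In the Sub-study 1c paragraph of Sample Size Justification, take the 66 participants of 1a/1b out of the medium-effect sentence.
2. Add for 1a and 1b: *With 27 (33) evaluable participants per arm, a single unadjusted two-sided 0.05 t-test comparison has 80% power for a standardized difference of about 0.78 (0.70), slightly larger for rank tests; if no event is seen in an arm, the one-sided 95% upper bound on its rate is 10.5% (8.7%).*
3. In Statistical Methods And Considerations, add risk differences with 95% confidence intervals to the adverse-event and other dichotomous safety summaries.
4. State there that a non-significant difference will not be taken as evidence of safety.

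The cost is wording and an extra table column. The stated sensitivity becomes less favourable, and the intervals will be wide: a hypothetical 3/27 against 3/27 gives a risk difference of 0 with a 95% interval (Newcombe) of −18 to +18 percentage points. No patients or visits are added.
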